## **Background and Rationale**

Asthma is the most common chronic disease of childhood. Characterized by airway inflammation and bronchial hyper-reactivity, affected patients can experience symptoms such as cough, shortness of breath, exercise limitation, and wheezing. Affected children are also at risk of developing acute exacerbations requiring healthcare utilization such as emergency department visits and/or hospital admission. An estimated 26 million Americans currently have asthma, including over 7 million children. This leads to over 14 million outpatient visits, nearly 2 million emergency department visits, and over 400,000 hospitalizations each year with a disproportionate number of these coming from low-income and minority populations. The estimated economic impact each year includes over \$50 billion in direct costs with an additional \$5.9 billion in indirect costs due to lost earnings. Uncontrolled asthma is associated with higher medical expenditures and health care utilization, decreased work productivity, and missed school days. There are multiple environmental factors that can trigger exacerbations including infections, weather changes, allergens, and airway irritants. Several of these triggers can be found in the home environment and when identified, reduction or removal leads to improvements in asthma morbidity. Current asthma guidelines recommend home environmental assessment and intervention as an important aspect of asthma management.

The majority of research in asthma trigger reduction has focused on inner-city populations with less work done in rural populations. While there may be a similar rate of asthma between these two populations, rural children may have a higher rate of undiagnosed asthma and asthma morbidity, often due to lack of available care. Nearly 50% of families living in rural areas have income less than 200% of the federal poverty level compared to 27% of those living in non-rural areas. Approximately 20% of these families lack insurance and as a result are less likely to receive preventive medical care. Less than 10% of physicians practice in rural areas and access to subspecialists is particularly difficult. When combined with the lack of insurance, rural populations are woefully underserved. Arkansas is a primarily rural state and also has large African American and other minority populations. In certain regions of the state, especially the Delta region, minority children with asthma suffered twice the mortality rate compared to the national average (45.0 vs 22.2 per 100,000) and had higher rates of asthma morbidity.

Telemedicine (TM) has recently evolved to address some of these concerns. TM involves the use of telecommunication systems to deliver health care at a distance which can improve access to care while reducing costs. In studies of heart failure, TM led to similar outcomes as in-person or phone visits, while in diabetes, TM led to improved blood sugar control. In asthma, TM programs have led to reductions in daily asthma symptoms and health care utilization. To date, TM has not been utilized in asthma home assessment programs. As with clinical care, TM could improve the access to this important aspect of asthma care while decreasing the costs associated with in-person programs. In this project, we aim to determine the effectiveness of TM asthma home assessments/interventions in reducing triggers in a cohort of underserved

Protocol v8 5/27/2021

Title: Efficacy of Telemedicine Home Assessments for Identification and Reduction of

Asthma Triggers

PI: [name]

Institution: University of Arkansas for Medical Sciences (UAMS) and Arkansas Children's Hospital/Research Institute (ACH/ACRI)

Sponsor: UAMS Translation Research Institute (UAMS TRI)

asthmatic children. Approximately 1500 children each year receive care at Arkansas Children's Hospital (ACH) for acute exacerbations of asthma. The majority of these children are African American and nearly 25% of these patients live below the federal poverty level. Given the burden of asthma in minority populations living in Arkansas, targeted home interventions could lead to significant reductions in asthma morbidity.

### **Hypothesis and Specific Aims:**

#### **Specific Aim 1: Compare the effectiveness of TM home**

**assessments/interventions versus standard of care education for the reduction of asthma related triggers.**

***Hypothesis 1:*** TM home assessments/interventions will lead to greater reductions in asthma-related triggers compared to standard of care education.

#### **Specific Aim 2: Determine changes in asthma morbidity as a result of asthma home assessments and related interventions.**

***Hypothesis 2:*** TM assessments/interventions will lead to greater reductions in asthma symptoms and healthcare utilizations related to acute asthma compared to standard of care trigger education.

### **Study Design and Procedures**

**Design Overview:** We will conduct a 6 month randomized pilot trial of 40 pediatric patients, ages,  $\geq 5$  and  $\leq 18$  years, with persistent asthma to compare trigger reduction performed through TM home assessments/interventions versus standard of care education. (**Figure 1**) For the proposed study, participants will be randomized to receive TM home assessments/interventions performed by a trained home visitor (HV) or standard of care asthma trigger education by the HV. Those who are randomized to TM home assessments/interventions will complete a baseline home assessment and two follow-up visits, occurring 2 months apart. Visits will assess the presence of potential asthma triggers in the home and frequency of asthma symptoms/exacerbations. TM participants will be provided education and materials necessary to reduce asthma triggers in the home. Follow-up visits will assess the interval change in presence of asthma triggers, change in daily asthma symptoms/exacerbations, and participant/family retention of education. For subjects randomized to receive standard of care asthma education, written and verbal information will be provided regarding identification and removal of potential asthma triggers in the home but no formal assessment of the home will be performed, nor will participants in this arm receive trigger reduction supplies. The **overarching hypothesis** is that utilization of telemedicine asthma home assessments/interventions will result in higher efficacy for trigger reduction, asthma outcomes, patient/family satisfaction, and retention of trigger education compared to standard of care asthma education.

### **Figure 1. Summary of Study Design**

[figure not shown]
Title: Efficacy of Telemedicine Home Assessments for Identification and Reduction of

Asthma Triggers

PI: [name]

Institution: University of Arkansas for Medical Sciences (UAMS) and Arkansas Children's Hospital/Research Institute (ACH/ACRI)

Sponsor: UAMS Translation Research Institute (UAMS TRI)

**Study population:** We will recruit 40 children (ages  $\geq 5$  and  $\leq 18$  years) with persistent asthma to participate in a prospective, randomized trial. Participants will be recruited from ACH locations including the emergency department, inpatient services, general, and/or asthma specialty (Allergy/Immunology, Asthma, Pulmonary) clinics.

**Screening and Eligibility:** A partial HIPAA waiver will be obtained to allow for access to identifiable health information in order to screen and recruit for this study. Patients will be pre-screened to determine age and persistent asthma diagnosis eligibility. The pre-screening process will involve the research staff reviewing the recruitment clinics, emergency department, and inpatient services daily EPIC schedules, to capture the age, diagnosis and potential participant's name, parent name, phone number and zip code. This information will be logged into a screening log in Excel. The screening log will be password protected and the research coordinator, study respiratory therapist and principal investigator will have access to this screening log. The research staff will call the potential participant/caregiver to provide a brief introduction (approximately 2 minutes) about the study. No additional PHI will be obtained during the introduction call. The purpose of the call is informative and to provide the potential participant/caregiver the opportunity to learn more about the research study during their scheduled clinic visit.

Patients identified as eligible for the study will be contacted and if interested in study participation, will be scheduled for a screening, enrollment, and initial demographic assessment visit to occur at the ACH campus.

**Inclusion Criteria:**

- 1) Age  $\geq 5$  years and  $\leq 18$  years
- 2) Have a diagnosis of persistent asthma as defined by national guidelines criteria
- 3) Patient receives care in ACH primary care, in patient and/or specialty clinics

Title: Efficacy of Telemedicine Home Assessments for Identification and Reduction of

Asthma Triggers

PI: [name]

Institution: University of Arkansas for Medical Sciences (UAMS) and Arkansas Children's Hospital/Research Institute (ACH/ACRI)

Sponsor: UAMS Translation Research Institute (UAMS TRI)

- 4) Patient has had at least one or more acute exacerbations of asthma within the 12 months prior to enrollment that led to an emergency department visit, hospital admission, or prescription for systemic steroids
- 5) English speaking participants/parents
- 6) Access to WIFI, smartphone or mobile device (tablet)

**Exclusion Criteria:**

- 1) Age <5 or >18 years
- 2) Non-English speaking participants/parents
- 3) Patients not receiving primary and/or asthma specialty care or inpatient services at ACH
- 4) Inability of patient or family to participate in TM evaluation due to lack of access to WiFi or smartphone or mobile device

***Rationale for only enrolling participants with persistent asthma:*** Only children with persistent asthma will be recruited to participate in the proposed study because they require regularly scheduled, follow-up to monitor asthma control and prevention of future exacerbations. Patients with intermittent asthma will not be recruited for participation because they typically are not at high risk of acute exacerbation nor require specialty care.

**Recruitment:** Potential participants will be recruited from ACH primary care or asthma subspecialty clinics through direct patient contact and advertising. These patients may also receive care in other ACH settings such as the emergency department, inpatient services or may be registered in institutional research participant databases, so we will recruit from these locations if needed to meet recruitment goals. Only one child per household who meets eligibility criteria will be enrolled.

We will utilize flyers, ACH/ACRI Intertube, and electronic signage to advertise the study. We will advertise via ACH/ACRI social media (i.e. Facebook, Twitter, and YouTube). The study will also be advertised via word of mouth. The advertisements will provide the contact information allowing parents/caregivers/potential adult participants to directly contact research staff. The clinics will be provided the study coordinator/respiratory therapist contact information to address any questions.

**Screening, initial demographic assessment and informed consent:** The informed consent/assent process will be carried out by trained research staff. All potential participants will be screened to ensure they meet inclusion and exclusion criteria as outlined above. After pre-screening, at or before the time of the potential participant's scheduled clinic visit, the research team will ask the parent/caregiver more detailed screening questions to determine eligibility prior to enrollment. The detailed screening may occur in person or via phone conversation from the research team's office or from a private, quiet area different from the research team's office. If eligible, informed consent/assent will be obtained from interested parents/caregivers/legal authorized

Title: Efficacy of Telemedicine Home Assessments for Identification and Reduction of

Asthma Triggers

PI: [name]

Institution: University of Arkansas for Medical Sciences (UAMS) and Arkansas Children's Hospital/Research Institute (ACH/ACRI)

Sponsor: UAMS Translation Research Institute (UAMS TRI)

representative and patients. Adolescents who reach the age of maturity (turn 18 years of age) while enrolled during the study period will be re-consented. The research staff will contact the parent/caregiver/legal authorized representative prior to the participant's age of maturity and a time will be scheduled to re-consent the participant using the IRB approved Informed Consent document. In addition to survey and home assessment data, we will obtain consent from caregivers and adult participants to access participants' health record to assess and monitor healthcare utilization for asthma. In the event a parent/potentially eligible participant agrees to participation at a later time after the eligibility screening, the informed consent interview and initial demographic assessment can be completed at an ACH campus location. During the consent/assent process, the participant will be given a copy of the consent document and asthma trigger education materials. Participant identification and enrollment will take place until we meet our enrollment goal.

**Randomization:** Subjects will be randomized 1:1 into 2 groups. One group will receive TM home assessments/interventions for identification and reduction of asthma triggers in the home while the other group will receive standard of care asthma trigger education. Randomization will occur at the time of enrollment visit after consent and assent is obtained and initial demographic assessment is complete. All participants will receive the same asthma education and trigger reduction materials. For those randomized to TM, participants will receive TM assessment of their home as well as an Asthma Home-Assessment kit that will provide supplies to reduce asthma triggers in the home.

**The Role, Qualifications, and Expectations of the Home Visitor (HV):** The Home visitor (HV) is a frontline public health worker who is a trusted member of and/or has an unusually close understanding of the community served. The HV is in a unique position to partner with families due to living in the area they are serving or having similar cultural backgrounds. The person acting in this role will be responsible for performing standard of care trigger education and asthma TM home assessments to aide in the identification and reduction of exposure to indoor asthma triggers. The goal is to establish a trusting partnership with participants and family members by providing education and tools to maximize asthma control and management as well as model appropriate behavior standards and core values as exemplified by Arkansas Children's mission and vision statement. For the purpose of this pilot project, the HV will enter into a contract agreement with UAMS or the Arkansas Children's Research Institute (ACRI) for the period of the pilot project. A minimum of a high school education, with a Bachelor degree in a health or social science related field preferred. In addition, one year of experience in some type of home visiting related to health care. Asthma specific training will be provided in the amount of 10 hours by a Certified Asthma Educator. The HV will receive CITI training as well. The education materials are provided by the Association of Asthma Educators and a certificate of completion is awarded after post testing. The HV will be expected to carry out the asthma home assessment via TM consistent with the procedures listed below.

Title: Efficacy of Telemedicine Home Assessments for Identification and Reduction of

Asthma Triggers

PI: [name]

Institution: University of Arkansas for Medical Sciences (UAMS) and Arkansas Children's Hospital/Research Institute (ACH/ACRI)

Sponsor: UAMS Translation Research Institute (UAMS TRI)

**Study Procedures, Outcome Measures, and Longitudinal Assessments:** For the proposed study, participants will receive home assessments for identification and reduction of asthma triggers via TM or standard of care asthma trigger education. Eligible subjects will undergo a total of 4 visits including an initial, in person screening/enrollment and initial demographic assessment visit, lasting approximately 1-2 hours. After enrollment and randomization, each TM participant will receive three home assessments including an initial baseline home assessment and two follow-up assessments, each 2 months apart (+/- two weeks). The home assessment visits will last approximately 90 minutes. During the TM home assessment, a home environmental asthma trigger assessment checklist (heat) will be utilized to identify potential asthma triggers in the subject's home. TM participants and their household will receive education and supplies, at the time of enrollment, for reduction of any identified triggers as well as education and supplies for general cleaning of the home. The Asthma Home Kit supplies provided to participants will include: Quickie 45TRI automatic sponge mop, child resistant roach and mice bait stations, zippered mattress covers, zippered pillow covers, trash can with lid, trash bags, anti-microbial sponges, rubber gloves, non-toxic all-purpose cleaner, Borax powder, scrubbing pads, Quickie home pro cleaning cloths, broom/dust pan, dusting spray, and paper towels. Each kit will contain labeled instructions on the proper use and/or storage of each item.

For those receiving standard of care education, each subject will receive the same education given to TM subjects for identification and reduction of asthma triggers, but will not receive TM home assessments or trigger reduction kits. Standard of care subjects will be contacted again at 2 months and 4 months (+/- 2 weeks) to assess retention of education materials and to provide additional asthma education and trigger reduction info. All participants will then receive a phone follow-up at 6 months (+/- two weeks) from the time of enrollment.

Dust samples will be collected from all subjects in both study arms. We will use the Dustream collector (Indoor Biotechnologies) to collect the dust specimens. Subjects will receive a dust collector kit that attaches to a vacuum cleaner. All participants will receive written instructions at the time of enrollment but will also be contacted by TM to assist with proper collection of the dust samples. These samples will be mailed to the study team using pre-paid postage and packaging through the USPS. One sample will be collected from the main living area and another sample will be collected from the participant's sleeping area during the baseline visit. A second set of dust samples will be collected at the 4 month visit for both groups.

Each participant will be contacted by phone at 6 months for an end of study visit. This phone conversation should last approximately 15-30 minutes. In the event the participant is no longer available on the day of the scheduled follow-up visits or 6-month phone contact, three attempts will be made to complete study procedures/ end of study phone call. If the research staff are unsuccessful after the third scheduled visit or phone call attempt, an email will be sent to the parent/caregiver asking that he/she contact the research staff via return phone call.

Protocol v8 5/27/2021

Title: Efficacy of Telemedicine Home Assessments for Identification and Reduction of

Asthma Triggers

PI: [name]

Institution: University of Arkansas for Medical Sciences (UAMS) and Arkansas Children's Hospital/Research Institute (ACH/ACRI)

Sponsor: UAMS Translation Research Institute (UAMS TRI)

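### Telemedicine households hold the trigger-reduction kit before the baseline dust sample is taken, and no visible text says to sample first or sets a sampling window in either arm

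*Combined protocol and SAP*

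**What the plan says.** Enrollment is a campus visit. Under Screening and Eligibility, interested patients "will be scheduled for a screening, enrollment, and initial demographic assessment visit to occur at the ACH campus". Under Randomization: "Randomization will occur at the time of enrollment visit after consent and assent is obtained and initial demographic assessment is complete". So the arm is known before the family goes home.

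Under Study Procedures, Outcome Measures, and Longitudinal Assessments, the TM arm gets its kit at that point: "TM participants and their household will receive education and supplies, at the time of enrollment, for reduction of any identified triggers". The kit includes mattress and pillow covers and cleaning supplies. After enrollment and randomization, "each TM participant will receive three home assessments including an initial baseline home assessment and two follow-up assessments". The standard-of-care (SOC) arm gets the same education "but will not receive TM home assessments or trigger reduction kits"; the Design Overview agrees ("nor will participants in this arm receive trigger reduction supplies").

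The dust paragraph of the same section takes baseline samples from the living area and the child's sleeping area at the baseline visit. Both arms have written instructions from enrollment and an undated TM contact to help with collection. The first-visit steps under Telemedicine Home Assessment begin with taking the items out of the kit; dust collection is not a listed step.

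The contacts at months 2, 4 and 6 carry a tolerance of two weeks either way. The baseline sample has none.

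**The concern.** The primary outcome compares dust mite levels at 4 months with baseline and between arms, so it needs a baseline that precedes the intervention in both arms. As written, one arm's intervention can be in the home before the baseline is measured, and the kit contains items that act on the areas sampled. Nothing visible tells the family to sample first.

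The second gap is the date of the sample. The interval from enrollment to the TM baseline assessment is not given. For SOC, the section names no baseline home assessment, and the first dated contact after enrollment is month 2. The two arms could therefore be sampled at different times after both have received trigger education.

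What is at stake is the size of the estimated effect, which is a main product of a 40-child pilot. No passage calls for the date of first kit use, so any early use could not be reliably measured afterwards, and no later analysis can restore a clean baseline.

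**Working it through.** **Order of events in the visible text**

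| Event | TM | SOC |
|---|---|---|
| Randomization | Enrollment visit, on campus | Same |
| Trigger education | From enrollment | From enrollment |
| Kit | At enrollment | None |
| Baseline dust | At home, baseline visit; no window | At home, baseline visit; contact not identified, no window |
| Rule to sample before kit use | None found | Not applicable |

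That the TM sample comes after the kit is an inference, but a firm one: the dust comes from the home, enrollment is on campus, and the TM home assessment follows enrollment.

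**The plan's own figure.** From the sample-size section: 20 per arm, difference 4 µg/g, SD 2, two-sided 5%. The standard error is 2 × sqrt(2/20) = 0.632, and 4/0.632 = 6.32. Power is then above 99.99%, so the stated value of at least 96% is true as a bound but is not reproduced as a value. This point does not depend on it.

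**Bias formula.** Let b_T and b_S be the average reductions (µg/g) already present at baseline sampling in TM and SOC. The expected estimate is:
- change score: 4 − (b_T − b_S)
- analysis of covariance with baseline as covariate: about 4 − rho × (b_T − b_S), where rho is the correlation between baseline and month 4 (equal SDs).

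The plan names a one-way analysis of covariance but not its covariate, so both forms are shown.

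**Early kit use only (b_S = 0).** Suppose k of the 20 TM families use the kit before sampling and a share s of their effect is present by then. Then f = (k/20) × s and b_T = 4f. The values of k, s and rho are assumptions; the documents give none. Example: k = 5 and s = 0.5 give f = 0.125, so the change score estimates 4 × 0.875 = 3.5. For the covariance analysis, 4 × (1 − 0.125 rho) = 3.85, 3.75 and 3.65 at rho 0.3, 0.5 and 0.7. Simulation (bivariate normal, 20,000 trials per case) gives slightly smaller losses when only some families shift, because the uneven shift widens the baseline spread and flattens the slope:

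| k, s | f | Change score | Covariance, rho 0.3 / 0.5 / 0.7 |
|---|---|---|---|
| 0 | 0 | 4.00 | 4.00 / 4.00 / 4.00 |
| 2, 0.5 | 0.05 | 3.80 | 3.94 / 3.90 / 3.87 |
| 5, 0.5 | 0.125 | 3.50 | 3.87 / 3.77 / 3.69 |
| 10, 0.5 | 0.25 | 3.00 | 3.73 / 3.55 / 3.38 |
| 20, 0.25 | 0.25 | 3.00 | 3.70 / 3.50 / 3.30 |

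At the plan's inputs, power in all these cases stays above 99.9% for the covariance analysis and at about 97% or more for the change score.

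**Unequal sampling times.** If SOC families sample later and have already acted on the education, b_S rises and the estimate rises with it. If TM families sample later, b_T rises and the estimate falls. The sign is that of b_S − b_T, and the documents do not fix it.

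**The case against.** The strongest reply is that the text places mitigation at the home visits. Outcome Measures describes mitigation in the TM group as done at each home visit. Supplies are tied to identified triggers, and identification happens during the assessment. The first-visit steps have the items taken out on video and their use explained. Inspecting items on camera changes nothing in a mattress. On this reading most kits are untouched when the dust is taken. Table 1 also fixes a nominal baseline, so only a tolerance is missing. Figure 1 and the written dust instructions, where a sample-first step might sit, cannot be seen. Finally, under analysis of covariance the milder cases move the estimate by 0.1 to 0.3, well inside that analysis's own 95% half-width of 1.24 to 0.93 (rho 0.3 to 0.7).

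Much of this stands, and it makes widespread early use unlikely. It does not close the gap. Each kit carries its own labeled instructions, part of the supplies is for general cleaning whatever triggers are found, and nothing asks the family to wait. Even at a visit run exactly as listed, unpacking comes first and no dust step precedes it. If the unseen material already states the order, the change shrinks to aligning the protocol text and dating the SOC sample.

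Three stronger readings are tempting, and the documents do not support them:
- **The withdrawal rule shows a long gap.** It allows replacement before the first home assessment, but a family can withdraw within a day, so the rule says nothing about the length of the interval.
- **Any bias would be conservative.** That holds for early kit use alone. Both arms receive trigger education at enrollment, so unequal sampling times could push the estimate either way.
- **Both arms get the kit.** The Randomization section says "All participants will receive the same asthma education and trigger reduction materials", but its next sentence gives the kit to TM, and two other passages deny it to SOC. The wording needs reconciling as a separate, minor matter.

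**Conclusion.** The point holds as a cheap improvement to the primary measurement. The visible text puts the kit in TM homes before the baseline dust sample, sets no order between sampling and kit use, gives no baseline window in either arm, and leaves the SOC baseline contact unnamed.

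A reader might infer that the TM baseline is contaminated. The documents show only that it could be. If 5 of 20 families had half their effect early, the estimate would fall from 4.0 to 3.5 µg/g with a change score, or to between 3.9 and 3.7 with baseline as covariate; with no early use it stays at 4.0. These figures rest on assumed values of k, s and rho and on the plan's difference of 4 and SD of 2. At those inputs the harm is to the size of the estimate, not to power. For unequal sampling times, neither size nor direction can be derived from the documents.

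**What to change.** - In the dust paragraph, in the first-visit steps under Telemedicine Home Assessment, and in the written dust instructions, make baseline dust collection the first step at home, completed before any kit item is used.
- Set the same short baseline sampling window after enrollment in both arms, and name the contact that serves as the SOC baseline visit.
- Record the sampling date in both arms and the date of first kit use in the TM arm.

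The cost is an ordering instruction, one window and two date fields, and TM families wait a short time before using the kit. Enrollment, randomization and kit handover stay as they are.

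As a side option, a comparison of 4-month levels without baseline would not be affected by the baseline sample. It is less precise: its 95% half-width is 2.024 × 0.632 = 1.28 µg/g, against 1.24 to 0.93 for analysis of covariance with a clean baseline. It does not replace sampling first.
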